We posit that practices that have more highly developed PA&E and better teamwork will more effectively activate patients with diabetes and/or CVD. In turn, we posit that more highly activated patients will be more likely to achieve improvements on patient-reported outcomes, patient care experiences, and clinical measures over time compared to less activated patients. We also will also examine the roles that patient advisory groups and primary care team use of performance feedback data play in influencing improvements in patient activation and outcomes of care over time.

Figure 1. Logic Model

We will engage patients and primary care practice teams within two accountable care organizations (ACOs). In each ACO, we will randomly select eight practices: four who score high on PA&E activities and four who score low. We will survey practice team members twice: once at baseline and one a year later. We will also conduct two site visits: one near the beginning of the study and one during the 13-18 month period of the study.

[figure not shown]
We will randomly select four high and four low PA&E sites within each ACO using a broad definition of PA&E activities including: (1) patient care outreach in regard to disease prevention and health promotion; (2) changes in the clinician-patient relationship, particularly in the areas of communication, motivational interviewing, and patient involvement in treatment care plans; (3) shared decision-making; (4) patient self-management of their condition(s); (5) end of life/advanced serious illness care patient engagement and family involvement; and (6) patient involvement in the overall design of care and in organization-wide efforts to improve the quality of care. See methods section for a description and Appendix I for an example of the instrument to be used for determining the “more highly involved” and “less highly involved” practices.

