To project the sample size requirements given 16 practices (8 high PA&E and 8 low PA&E), we estimated the design effect (DE) to account for the clustering of patients within practice sites. While PROMIS data from participating ACO patients are presently unavailable, recent studies of change over time on the PROMIS physical functioning measure informed our sample size estimates for the PROMIS measure⁴⁷. Having been selected using item-response theory (IRT) methods and extensive testing, the PROMIS physical functioning measure is a precise measure that is sensitive to small changes in physical functioning over time. Given the published estimates and a range of design effect estimates (intraclass correlation (ICC)=0.01-0.04) to account for the clustering of patients within practices, a clinically meaningful change (e.g.,

PRINCIPAL INVESTIGATOR (LAST, FIRST, MIDDLE): [name]

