a 3-5 point change out of 100) on the PROMIS physical functioning measure can be detected with 50-65 patients per practice. Based on prior experience, we expect a minimum 50% response rate for completing the first patient survey and a 65% response rate for the second survey. We expect a 3% rate for undeliverable addresses and a 20% drop-out rate between the two survey periods based on our previous research. Patient-level blood pressure data from adult diabetic patients at HCP ACO practices were used to calculate the design effect (ICC=0.01-0.02). Previous research suggests that population-level improvements in blood pressure on the order of 3-5 mm Hg are clinically meaningful⁴⁸⁻⁵⁰. Based on a two-sided difference of means with a power of 0.90, we estimate that an average of 140 patients per practice are needed to detect a 3 mm Hg difference in change in systolic blood pressure over time between the high (n=8) vs. low (n=8) PA&E practices. Based on these calculations, we will randomly select 273 patients per practice (n=4,368) with diabetes or CVD diagnoses from each of the practice sites and teams in the two ACOs for inclusion in the study. Given the assumptions of response rates and attrition noted above, this will yield a final total of 1102 patients with two time points for analysis of the PROMIS (69 patients per site). In addition we expect to receive retrospective clinical outcomes data from the EHR for most of the sampled patients (n=4,368). Thus, even with slightly lower than expected survey response rates, our study will be sufficiently powered to detect clinically meaningful differences between high and low PA&E practices on both patient-reported (PROMIS) and clinical, e.g., blood pressure, outcome measures.

MEASURES

Measurement of Site PA&E Activities

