Analyses Addressing Aim 1. At each of the two cross-sections for the patient and teamwork assessment surveys, we will clean the data, examine their distributions, and conduct psychometric analysis to assess the reliability and validity of the measures. After composite variables have been constructed and properties assessed, we will examine the cross-sectional relation of PA&E activities, teamwork assessment results, and patient survey results. Using a dichotomized variable derived from baseline responses to the PA&E Practice Site Assessment Survey (see Appendix I), we will categorize sites as “high” or “low” PA&E based on the response distributions in our data. We will then assess association of key measures in two stages. In the first equation, using linear regression models, we will examine the PAM as a function of high vs. low PA&E (site level), controlling for practice size, and for patient casemix adjustment variables previously used in research that has compared organizations on patient experience and clinical quality measures^{79, 80}. Casemix factors to be considered include age, sex, educational attainment, and comorbid health conditions. We will then examine the patient reported outcome (PRO) measures, patient experience (PE) and the clinical measures as a function of the PAM, PA&E level (at site level), practice size, and casemix using multilevel regression models to account for the clustering of patients within practices. The simplified equations are:

$$PAM = Hi / lowPA \& E + PracticeSize + Casemix + \epsilon$$

$$PE = Hi / lowPA \& E + PAM + PracticeSize + Casemix + \epsilon$$

$$PRO = Hi / lowPA \& E + PAM + PracticeSize + Casemix + \epsilon$$

$$ClinMeasures = Hi / lowPA \& E + PAM + PracticeSize + Casemix + \epsilon$$

Aim 2. To assess whether the relation of PA&E activities and better PROs and clinical outcomes is stronger for more highly activated patients than less activated patients at baseline.

Analyses Addressing Aim 2. To address the extent to which PA&E activities conducted by the practice are more influential in improving PROs and patient experience among patients with high PAM levels at baseline, we will extend the Aim 1 analyses. Specifically, we will use multilevel regression with site random effects to model changes in PROs and the clinical measures over time as a function of baseline PAM scores, practice size, patient casemix, PA&E, and then by interacting PA&E and the PAM scores. The simplified equations are:

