$$PE = Hi / lowPA \& E + PracticeSize + PAM + PA \& E * PAM + Casemix + \epsilon$$

$$PRO = Hi / lowPA \& E + PracticeSize + PAM + PA \& E * PAM + Casemix + \epsilon$$

$$ClinMeasures = Hi / lowPA \& E + PracticeSize + PAM + PA \& E * PAM + Casemix + \epsilon$$

We will explore differences between the two extreme PAM categories (level 1=lowest activation, 4=highest activation) in addition to examining the continuous PAM measures, as we expect the biggest differences over time differences in PRO and patient experience between patients with highest and lowest baseline PAM scores.

PRINCIPAL INVESTIGATOR (LAST, FIRST, MIDDLE): [name]

Aim 3. To assess the stability of the PA&E-outcome relationship over two measurement periods at the individual and practice-level;

Analyses addressing Aim 3. After both waves of data collection are completed, we will assess the consistency of the results at two levels- patient-level and practice-level. We will compare the regression coefficients for models at each wave to examine differences in associations of the independent variables with outcomes at each cross-section.

Aim 4. To assess changes over time (T1 vs. T2) in patient-reported outcomes of care, patient experience and clinical measures, as a function of changes over time in PA&E activities, patient activation, controlling for patient casemix.

Analyses Addressing Aim 4. We will integrate the patient survey results and the patient level results at the practice level. We will examine 'over time' effects using three approaches: 1) multilevel regression with interaction term as specified here, 2) stratified by low vs. high PA&E practices and looking at coefficient differences, 3) lagged regression (using T1 to predict T2) vs. change in T1 and T2 predicting T2), etc. The simplified equations below provide a multilevel framework for studying the impact of site PA&E activities on patient activation, patients' experiences, and patient-reported outcomes over time:

$$\Delta PRO = \Delta PA \& E + \Delta PAM + \varepsilon$$

$$\Delta PE = \Delta PA \& E + \Delta PAM + \varepsilon$$

$$\Delta ClinMeasures = \Delta PA \& E + \Delta PAM + \varepsilon$$

Given the uncertainty in distribution and variation, we will examine the inclusion of other relevant predictors including fixed effects for casemix and practice size.

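### The Aim 1 model for patient activation (PAM) is specified without practice clustering, although its exposure varies only between 16 practices

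*Combined protocol and SAP*

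**What the plan says.** The Analysis Section describes Aim 1 in two stages and gives each its own method. For the first stage: "In the first equation, using linear regression models, we will examine the PAM as a function of high vs. low PA&E (site level"), with practice size and casemix as covariates. For the second, the patient-reported, experience and clinical measures are modelled "using multilevel regression models to account for the clustering of patients within practices". The clustering clause belongs to the second stage only.

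The other relevant places are these:

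- The Research Plan posits that "practices that have more highly developed PA&E and better teamwork will more effectively activate patients". The PAM equation is the written test of that link.
- Analyses Addressing Aim 2: "we will use multilevel regression with site random effects to model changes in PROs and the clinical measures over time". PAM is a predictor there, not the outcome.
- Analyses Addressing Aim 4: "The simplified equations below provide a multilevel framework for studying the impact of site PA&E activities on patient activation". The three equations that follow have change in patient-reported outcomes, experience and clinical measures on the left-hand side; none has PAM.
- Health Care Team Selection says that analysis will be at practice level, in contrast to the team-level scores fed back to practices. It names no method.
- Patient Selection treats clustering as material, with a "range of design effect estimates (intraclass correlation (ICC)=0.01-0.04) to account for the clustering of patients within practices" for PROMIS. For blood pressure: "Patient-level blood pressure data from adult diabetic patients at HCP ACO practices were used to calculate the design effect (ICC=0.01-0.02").

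**The concern.** Whether a patient counts as high or low PA&E is decided entirely by the practice. The comparison therefore rests on 16 units, not on the number of completed questionnaires. An ordinary linear regression counts patients, so any tendency of patients in one practice to resemble each other makes the standard error too small. An analyst following the text would put a practice term in three of the four Aim 1 models and leave it out of the fourth.

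At stake is the first step of the logic model: whether practices with more PA&E have more activated patients. A chance difference among 16 practices could be reported as an effect of PA&E on activation. Written equations number 11 (4 for Aim 1, 3 for Aim 2, 3 for Aim 4, 1 for Aim 5), and only this one has PAM as its outcome. It is to be fitted at both survey waves.

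**Working it through.** **Inputs.** Patient Selection gives 273 patients in each of 16 practices (4,368), 3% undeliverable, 50% response at wave 1, 20% dropout and 65% response at wave 2. ICCs are 0.01–0.04 (PROMIS) and 0.01–0.02 (blood pressure). Two inputs are assumed: a two-sided alpha of 0.05, and a PAM ICC in the plan's range for other outcomes. Lower values are shown too.

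**Reproducing the plan's figure.** 4,368 × 0.97 × 0.50 × 0.80 × 0.65 = 1,101.6, and 1,101.6/16 = 68.9. This matches the stated 1102 and 69 per practice. Wave 1 respondents: 4,368 × 0.97 × 0.50 = 2,118, or m = 132.4 per practice.

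**Effect of ignoring practice.** Design effect DE = 1 + (m − 1) × ICC. The unclustered standard error is 1/√DE of the correct one. The actual error rate of a nominal 5% test is 2 × [1 − Φ(1.96/√DE)].

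| ICC | Wave 1 DE | Wave 1 error | Wave 2 DE | Wave 2 error |
|---|---|---|---|---|
| 0 | 1 | 5% | 1 | 5% |
| 0.005 | 1.66 | 12.8% | 1.34 | 9.0% |
| 0.01 | 2.31 | 19.8% | 1.68 | 13.0% |
| 0.02 | 3.63 | 30.3% | 2.36 | 20.2% |
| 0.04 | 6.26 | 43.3% | 3.71 | 30.9% |

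At ICC 0.01 / 0.02 / 0.04 the unclustered standard error is 66% / 53% / 40% of the correct one at wave 1, and 77% / 65% / 52% at wave 2.

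**ICC at which error reaches 10%.** Setting 1.96/√DE = 1.645 gives ICC = [(1.96/1.645)² − 1]/(m − 1). That is 0.0032 at wave 1 and 0.0062 at wave 2, both below the lowest ICC in the plan.

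**Simulation check.** With 8 + 8 practices and practice size in the model (20,000 runs per cell), the unclustered model rejected as follows at ICC 0.005 / 0.01 / 0.02 / 0.04:

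- wave 1: 12.7 / 19.7 / 30.6 / 43.5%
- wave 2: 9.3 / 13.0 / 20.5 / 31.3%

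A practice-level test on 13 df rejected 4.8–5.3% of the time. A second simulation added four patient-level casemix covariates (2,500 runs per cell, ICC 0 to 0.04). The 13-df test then gave 4.1–5.8%, and the same standard error with a 1.96 cut-off gave 6.3–8.0%.

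**Cost in precision at wave 1.** Ignoring practice size, the 95% half-width in SD units is 1.96 × √(4/2,118) = 0.085 unclustered. On 13 df (critical value 2.160) it is 2.160 × √(4 × 2.31/2,118) = 0.143 at ICC 0.01 and 2.160 × √(4 × 6.26/2,118) = 0.235 at ICC 0.04. With practice size in the model, as planned, the simulated mean half-widths are 0.089, 0.146 and about 0.24.

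**The case against.** The best case on the other side is that this is shorthand. The equations are labelled simplified. All four Aim 1 equations show a single error term, including the three that are multilevel, and a linear model can carry a random intercept. Nowhere does the plan say that clustering will be ignored, and the practice-level remark under Health Care Team Selection may show the intent. This is fair about intent, and it means that the finding rests on the prose, not on the equations. But the prose gives the two stages different methods, and no passage names a clustering method for a PAM outcome.

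The size can also be questioned. Each ACO supplies four high and four low practices, so differences between ACOs in PAM cancel from the contrast. If half of the between-practice variance lay between ACOs (an illustration; the share is unknown), simulated error for ICC 0.01–0.04 would be about 13–31% at wave 1 and 9–21% at wave 2. The inflation is smaller but remains. In that scenario a practice-mean test with no ACO term is conservative, rejecting 1–3% of the time. The 13 df should therefore be recounted if an ACO term is added.

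Two further points stand. The simulated practice-level test used practice means (casemix-adjusted in the second simulation) in a balanced design, as a stand-in for the random-intercept model; real response will vary by practice. And the plan states no degrees of freedom for the other three Aim 1 models either, so that part of the remedy is not peculiar to PAM.

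Finally, PAM is an intermediate step and not a named Aim 1 outcome. That limits the consequence but does not make the stated method correct.

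**Conclusion.** The concern holds. As written, the Aim 1 PAM model names no allowance for practice, and following it would give standard errors that are too small for an exposure set at 16 practices. If the PAM ICC is 0.01–0.04 and alpha is two-sided 0.05, the false-positive rate is about 20–43% at wave 1 and 13–31% at wave 2. At the plan's blood pressure ICCs it is 20–30% and 13–20%. These figures are conditional: the documents give neither a PAM ICC nor an alpha, ACO stratification could lower the inflation, and at ICC 0 there is none. Very little clustering is needed for a material effect, however. The problem is confined to this one equation, and the other three Aim 1 models already name clustering. It should be fixed before analysis, but it does not undermine the study.

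**What to change.** Add one sentence to Analyses Addressing Aim 1: the PAM equation is fitted as a multilevel model with the same practice random intercept as the other three, and its PA&E coefficient is tested on practice-level degrees of freedom. With intercept, PA&E and practice size at practice level, that is 16 − 3 = 13; an ACO term would make it 16 − 4 = 12. Wording the degrees-of-freedom clause to cover all four Aim 1 equations would cost nothing more.

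No new data or sample size change is needed. The only cost is a wider interval for the PAM contrast: at wave 1 the half-width goes from 0.089 SD to 0.146 SD at ICC 0.01, or to about 0.24 SD at ICC 0.04. If a multilevel model was intended all along, the sentence simply removes the ambiguity.

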We will collect patient demographic information as part of the patient surveys, including patient age, sex, race, ethnicity, self-rated English proficiency, preferred language, interpreter use, employment status, marital status, education, and military status. We will supplement these survey data with information about patient age and sex from ACO clinical and sociodemographic data submitted to Berkeley as part of the project.

TEAMWORK ASSESSMENT INSTRUMENTS

Primary care team members from each of the 16 practices will complete the following instruments that we refer to as "teamwork assessment instruments." These are: (1) team culture, (2) team leadership, (3) relational coordination, and (4) perceived team effectiveness. These will be completed at baseline (0-3 months) and then again at 18 months.

Implementation of the teamwork assessments will be overseen by a data coordinator at each ACO paid in part by the grant.

An important component of the project is to provide primary care teams and patient advisory groups with feedback on their patient's reports of physical functioning, social functioning, and experiences of primary care. As primary care practices embark on integrating new roles and responsibilities for non-physician clinicians and staff for improving patient activation and engagement, supportive practice environments that foster organizational learning and effective teamwork are essential.^{63, 64} Providing primary care teams with performance feedback on patient-reported outcomes, patient experience, and clinical quality of care measures is one important way of fostering a shared responsibility for patient care among interdisciplinary members^{65, 66} and supporting a measured approach to team performance improvement efforts.⁶⁷ When teams do not receive feedback on their collective work, members often encounter difficulties working together to modify existing workflows and procedures^{68, 69}. Consequently, team feedback on patient experience and PRO data and teamwork assessment can aid primary care teams in their process improvement efforts. The limited amount of performance feedback available to primary care teams on their patients' experiences and patient-reported outcome measures⁷⁰ can have important downstream consequences for patient care, including less patient-centered clinician-patient communication and self-management support.

PRINCIPAL INVESTIGATOR (LAST, FIRST, MIDDLE): [name]

Team Composition Assessment

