HealthCare Partners ACO was formed in 2010 as one of the early Dartmouth-Brookings demonstration ACOs⁴⁶. They hold both CMS and private payer risk-based contracts collectively accountable for 50,000 lives. They serve high proportions of Medicaid patients in low-income communities who tend to face many social and financial barriers to self-management of diabetes and CVD. Approximately 55% of HCP's Southern California patients are Latino. HCP and the HCP Institute for Applied Research and Education have extensive expertise leading patient-centered HIT development and research projects. For the past 3 years, the HCP Institute through earned, competitive grant funding, has been refining the application of remote patient monitoring of chronic disease in older adult patients using interactive voice response technology (IVR). Based on a third-party evaluation by the Center for Connected Health at Partners Healthcare in Boston, HCP's IVR system resulted in significant improvements in appropriate care⁸⁶. HCP's implementation of patient-centered HIT, particularly focused on integrating informal caregivers⁸⁷, are important patient activation and engagement innovations to study in the context of improving patient-reported outcomes, as there is considerable variation in the use of patient-centered HIT across HCP's practices. They are highly committed to this study as indicated by their letter of support and related materials in this proposal.

PRINCIPAL INVESTIGATOR (LAST, FIRST, MIDDLE): [name]

Both Advocate and HealthCare Partners will subcontract with UC Berkeley to perform the following tasks:

Securely transmit names, addresses, and contact information for 273 adult patients with diabetes and/or cardiovascular disease with at least 2 visits in the baseline year (2013) from each of eight primary care practices affiliated with our Accountable Care Organization (ACO) to the patient survey vendor selected for the project.

Securely transmit a de-identified patient-level data to the UC Berkeley research team in Months 7 and 19 covering 2013 and 2014 period, respectively. These datasets will include adult patients with diabetes and cardiovascular disease with at least 2 visits in the baseline year (2014) and the data elements include select sociodemographic information and clinical care process and outcome data using Healthcare Effectiveness Data Information Set (HEDIS) definitions for measures of chronic illness care.

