Appendix II. Patient Activation, Self-Reported Outcomes of Care, and Patient Experience
 (Number of questions = 65)

Measure	Item Count	Example Content	Internal Consistency Reliability	Why Selected (Why alternatives were not?)
Physical Function (PROMIS Short Form 12a)	13	
 • Are you able to do yard work like raking leaves, weeding, or pushing a lawn mower? • Are you able to bend down and pick up clothing from the floor? • Are you able to push open a heavy door? 	0.86-0.95	Research indicates that the PROMIS physical function composite, which is comprised of item response theory-based items, can result in greater responsiveness and precision across a broader range of physical function compared to other physical function measures. This can reduce sample size requirements and thus study costs. ⁹³
Demographics	11	Age, gender, race, ethnicity, self-rated English literacy, preferred language, interpreter use, employment status, marital status, education, and military status		Census specifications will be used, when applicable.

PRINCIPAL INVESTIGATOR (LAST, FIRST, MIDDLE): [name]

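### The Aim 1 clinical model needs the survey-only PAM score, so the high-versus-low comparison of BP, HbA1c and LDL-C runs in survey responders and not in the full EHR sample

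*Combined protocol and SAP*

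**What the plan says.** **Sample and power (Patient Selection).** The plan states that "we will randomly select 273 patients per practice (n=4,368) with diabetes or CVD diagnoses". For a 3 mm Hg difference in systolic change between 8 high and 8 low practices, at two-sided power 0.90, "we estimate that an average of 140 patients per practice are needed". On the survey, "we expect a minimum 50% response rate for completing the first patient survey and a 65% response rate for the second survey". On the EHR, "In addition we expect to receive retrospective clinical outcomes data from the EHR for most of the sampled patients (n=4,368"); the parallel text under Protection of Human Subjects (UC Berkeley) says all sampled patients. Both places conclude that clinical power would survive a somewhat poorer survey response.

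**Models (Analysis Section).** In Aim 1 the clinical measures are regressed on high/low PA&E, PAM, practice size and casemix. On casemix: "Casemix factors to be considered include age, sex, educational attainment, and comorbid health conditions". The Aim 2 clinical equation adds a PA&E-by-PAM interaction. The Aim 4 clinical equation uses change in PA&E and change in PAM.

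**Sources of the covariates.** PAM comes from the mailed or telephone survey. Education appears only among the survey demographics (Appendix II: "interpreter use, employment status, marital status, education, and military status"). Under Patient Demographics, "We will supplement these survey data with information about patient age and sex from ACO clinical and sociodemographic data". The ACO extract is described as "select sociodemographic information and clinical care process and outcome data" on HEDIS definitions. No source is named for comorbidity.

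**The concern.** The sample-size argument treats the clinical endpoints as independent of survey response, but the models do not. A patient who never returns the survey has a blood pressure in the EHR and no PAM score, so without a missing-covariate method that patient drops out of every displayed clinical equation. Three things are at stake.

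- **The population.** Aim 1 asks about patients of high and low PA&E practices. The model as written answers for those patients who respond, and willingness to respond may well be related to activation.
- **The estimand.** The logic model has PA&E acting on outcomes through activation, and the first Aim 1 equation treats PAM as a result of PA&E. Conditioning on PAM removes that route from the high/low coefficient. The overall clinical difference between high and low practices is never specified.
- **Confounding control.** Practices are not randomised to PA&E level, so a confounder that the plan names should have a named source.

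**Working it through.** **Inputs.** From Patient Selection: 273 sampled in each of 16 practices; 3% undeliverable; 50% and 65% response at waves 1 and 2; 20% drop-out between waves; 140 per practice needed; difference 3 mm Hg; power 0.90; ICC 0.01 to 0.02; 8 practices per arm. Alpha and the SD of systolic change are not given. I assume two-sided alpha 0.05 and solve for the SD.

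**1. The plan's own yield.** 4,368 x 0.97 x 0.50 x 0.65 x 0.80 = 1,101.6, and 1,101.6 / 16 = 68.9. This reproduces the stated 1102 and 69 per practice.

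**2. Patients who can enter a baseline-PAM model (Aims 1 and 2).** 273 x 0.97 x 0.50 = 132.4 per practice, or 2,118 in all. That is 48.5% of the sample. It is 7.6 below 140 (5.4%). Ignoring undeliverable mail gives 136.5, still 2.5% below.

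**3. SD implied by the 140.** With m patients per practice, effective n per arm = 8m / (1 + (m - 1) x ICC), and SD = 3 x sqrt(n_eff / 2) / (1.960 + 1.282).
- ICC 0.01: 1,120 / 2.39 = 468.6, so SD = 14.2 mm Hg.
- ICC 0.02: 1,120 / 3.78 = 296.3, so SD = 11.3 mm Hg.

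**4. Power for 3 mm Hg at those SDs** (normal approximation):

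| Patients per practice | ICC 0.01 | ICC 0.02 |
|---|---|---|
| 273 (all sampled) | 0.952 | 0.934 |
| 140 (plan's requirement) | 0.900 | 0.900 |
| 132.4 (wave 1 responders) | 0.893 | 0.896 |
| 68.9 (both waves) | 0.774 | 0.821 |

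A t-based version with 14 degrees of freedom gives SDs of 13.2 and 10.5 and powers within 0.001 of these.

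**5. Break-even.** Reaching 140 with baseline PAM needs a wave 1 response of 140 / (273 x 0.97) = 52.9%. At the planned 50% the count is already slightly short, so the claimed tolerance of a lower response does not carry over to models that contain PAM.

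**6. Comorbidity.** The modules listed in Appendix II are PAM 13, PACIC 11, care team experience 5, social roles 8, PHQ-4 4, physical function 13 and demographics 11. They sum to 65, the stated survey length, with no comorbidity module. The ACO extract does not name one either.

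**The case against.** The strongest reply is that little power is lost where it counts. The displayed model closest to the power calculation (change over time, high/low PA&E, baseline PAM) keeps power of about 0.89 to 0.90. The plan calls 50% a minimum, and the gap closes at about 53%. This stands, so the point should not be argued as a power failure.

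A reader might infer that the clinical endpoints in general fall to power of 0.77 to 0.82. The documents do not support that. The 69 per practice belongs to the Aim 4 change-in-PAM equation, which has no high/low term, is one of several approaches listed for that aim, and needs both surveys by the nature of its question. Aim 2 likewise needs PAM because it asks about effect modification by PAM.

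A reader might also infer that comorbidity is collected for nobody, or that education is ruled out for non-responders. Neither follows. Diabetes and CVD codes define the sample, PHQ-4 covers depression and anxiety in responders, and the extract's fields are described openly. The accurate statement is that no source is specified. Education and comorbidity are also only candidates for casemix, and the equations are labelled simplified, so PAM is the firm constraint.

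Finally, excluding non-responders is inferred from the plan's silence on missing covariates. That is fair, but the silence leaves the gap open.

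**Conclusion.** The point holds for the Aim 1 comparison of clinical measures. As specified, it rests on about 132 of 273 sampled patients per practice, although the plan expects EHR outcomes for most or all of them. Using them all would give power of about 0.93 to 0.95 against 0.89 to 0.90, a modest gain. The larger costs are exposure to non-response selection and the absence of any clinical estimate that is not conditional on PAM.

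The counts rest on the plan's response rates and on analysis of available data. The powers also rest on an assumed alpha of 0.05 and a back-solved SD. The 140 is itself only an approximate benchmark: it concerns a mean systolic change, whereas the Clinical Measures section defines percentages controlled within disease subsets, where usable numbers would be smaller.

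**What to change.** 1. For the clinical measures, make the main Aim 1 high-versus-low analysis a multilevel model without PAM, fitted to all sampled patients with EHR data. Adjust for practice size and for covariates available on all of them: age, sex and diagnosis-based comorbidity.
2. Keep the models with PAM and education as responder analyses. Report each with its own N, and do not extend the Patient Selection power statement to them, in particular not to the Aim 4 change-in-PAM model with about 69 per practice.
3. Name diagnosis-based comorbidity among the data elements of the ACO extracts, in both the human-subjects section for the two ACOs and the Consortium Contractual Arrangements.

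The cost is some analysis wording and a few fields in extracts that are already planned. The downside is that the all-patient model will not adjust for education unless the ACO extract can supply it.
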